Administrative Letter 06	25-Jan-2017	Changed MM Address
Revised Protocol 05	08-Dec-2015	Incorporates Amendment 06
Amendment 06	08-Dec-2015	Adds dosing windows to the Time and Events Schedule
Revised Protocol 04	28-Oct-2015	Incorporates Administrative Letter 05 and Amendment 05
Amendment 05	28-Oct-2015	
 To provide further clarity on the requirements for lipase testing To provide clarity on dose calculations To allow the EQ-5D-3L to be completed without an office visit if one is not otherwise needed.
Administrative Letter 05	23-Jul-2015	
 The of expectations when lipase results are not available prior to dosing Aligning the footnotes of Table 5.1-2 and Section 5.3, Safety Assessments with the requirements for lipase described in Table 5.1-2. Assessments allowed to be done according to standard of care At what cycle assessments should start and assessment windows When RECIST 1.1 criteria must be used. 
NOTE: Administrative Letter 04 was not finalized because it was considered to not be needed. However, Administrative Letter 05 was created and finalized with the mistaken understanding that Administrative Letter 04 was finalized.

Revised Protocol 03	02-Jun-2015	Incorporates Amendment 04
Amendment 04	02-Jun-2015	Decreases sample size
Revised Protocol 02	19-Mar-2015	Incorporates Amendment 03
Amendment 03	19-Mar-2015	This Amendment removes the inclusion of the treatment-naïve patients, also referred to as the first-line cohort.
Revised Protocol 01	16-Jan-2015	Incorporates Amendment 02 and Administrative Letter 03.
Amendment 02	16-Jan-2015	
 The inclusion criteria have been expanded and the exclusion criteria have been minimized. The study rationale also offers greater support for the expanded

Document	Date of Issue	Summary of Change
		
subject population.
 
 • Treatment-naïve patients have been added. • The options for palliative local therapy have also been expanded to meet the needs of the current patient populations. • The EORTC QLQ-C30 has been eliminated from the patients' follow up. • The time points and frequency of assessments have been updated. • The subjects in Cohort 2 will now be analyzed at the same frequency to Cohort 1, so the separate Time and Events Schedule for Cohort 2 was removed. • The statistical section has been reformatted to aid understanding of the analyses to support the respective primary, secondary, [REDACTED] objectives. • The timing and frequency of all assessments have been removed from sections of the protocol outside of the Time and Events tables. • The endpoints are more representative of the data that will be collected in support of the objectives. • The requirement for electrocardiograms has been removed.
Administrative Letter 03	02-Oct-2014	Correct the tables in Section 5.1, Flow Chart/Time and Events Schedule so that the information in these tables is consistent with the text in the protocol.
Revised Protocol 01a	04-Jun-2014	Incorporates Administrative Letter 01, Administrative Letter 02, and Amendment 01.
Amendment 01	04-Jun-2014	Revisions aim to comply with the Health Authority requirements in Germany
Administrative Letter 02	21-May-2014	A number was missing from Exclusion Criterion 4cviii. This letter is to provide you with the missing number. This is an administrative protocol change and does not significantly affect the safety of subjects, study scope, or scientific quality of a Phase IIb. Accordingly, it may be implemented immediately.
Administrative Letter 01	12-May-2014	The title of this protocol has been modified for consistency with the BMS conventions for protocols in the nivolumab program. This is an administrative protocol change and does not significantly affect the safety of subjects, study scope, or scientific quality of a Phase II or III protocol. Accordingly, it may be implemented immediately.
Original Protocol	18-Apr-2014	Not applicable

SYNOPSIS

Clinical Protocol CA209172

Protocol Title: A Single-Arm, Open-Label, Multicenter Clinical Trial with Nivolumab (BMS-936558) for Subjects with Histologically Confirmed Stage III (unresectable) or Stage IV Melanoma Progressing After Prior Treatment Containing an Anti-CTLA-4 Monoclonal Antibody **CheckMate 172: CHECK**point pathway and nivolu**MAb** clinical Trial Evaluation 172

Investigational Product(s), Dose and Mode of Administration, Duration of Treatment with Investigational Product(s): Nivolumab solution for injection, 3 mg/kg intravenous (IV) infusion over 60 minutes every 2 weeks for a maximum of 24 months

Study Phase: II

Research Hypothesis: High-grade (CTCAE v4.0 Grade 3 or higher), treatment-related, select adverse events occur with a low frequency in patients with histologically-confirmed, stage III (unresectable) or stage IV melanoma treated and progression after prior treatment containing an anti-CTLA-4 monoclonal antibody with nivolumab monotherapy.

Objectives:

The primary objective of this trial is to determine the incidence of high-grade (CTCAE v4.0 Grade 3 or higher), treatment-related, select adverse events in patients with histologically confirmed stage III (unresectable) or stage IV melanoma and progression after prior treatment containing an anti-CTLA-4 monoclonal antibody.

The secondary objectives of this study are:

- To determine the incidence and to characterize the outcome of all high-grade (CTCAE v4.0 Grade 3 or higher), select adverse events in patients with histologically confirmed stage III (unresectable) or stage IV melanoma and progression after prior treatment containing an anti-CTLA-4 antibody, treated with nivolumab monotherapy.
- To estimate overall survival (OS) in all treated subjects
- To estimate Investigator-assessed objective response rate (ORR)

[REDACTED]

[REDACTED]

[REDACTED]

[REDACTED]

[figure not shown]
[REDACTED]

[REDACTED]

Study Design: The study will include patients with histologically-confirmed stage III (unresectable) or stage IV advanced melanoma who have documented progression after treatment containing an anti-CTLA-4 monoclonal antibody. Patients will be treated with 3 mg/kg of nivolumab IV every 2 weeks for a maximum of 24 months. Patients will undergo screening evaluations to determine eligibility within 6 weeks prior to first dose following the signing of an informed consent. Each 14-day dosing period will constitute a cycle.

The Scientific Steering Committee will evaluate the clinical risk/benefit ratio closely following a defined Safety Management Plan.

Study Schematic:

Study Population:

Key inclusion criteria:

Patients with progression after prior treatment containing an anti-CTLA-4 monoclonal antibody (Cohorts 1 and 2):

- a) Patients with histologically confirmed malignant melanoma
- b) Eastern Cooperative Oncology Group (ECOG) Performance Status (PS):

- i) PS 0 to 1 (Cohort 1)
- ii) PS 2 (Cohort 2; a minimum of 50 patients and maximum of 185; clinical risk benefit ratio of Cohort 2 will be monitored by the Scientific Steering Committee)
- c) Previously treated unresectable stage III or stage IV melanoma as per the American Joint Committee on Cancer 2010 Guidelines regardless of BRAF mutation status
- d) Patients must have experienced disease progression or recurrence after prior treatment containing an anti-CTLA-4 monoclonal antibody
- e) Prior treatment with chemotherapy, interferon (adjuvant setting), IL-2, BRAF/MEK inhibitors for subjects with known BRAF mutations, MEK inhibitors for NRAS mutations, and cKIT inhibitor subjects with known cKIT mutations are allowed
- f) Patients with CNS metastases:
 - i) Patients are eligible if CNS metastases are treated and subjects are neurologically returned to baseline (except for residual signs or symptoms related to the CNS treatment) for at least 2 weeks prior to enrollment. In addition, patients must be either off corticosteroids or on a stable or decreasing dose ≤ 10 mg daily prednisone (or equivalent)
OR
 - ii) Patients are eligible if they have previously untreated CNS metastases and are neurologically asymptomatic. In addition, patients must be either off corticosteroids or on a stable or decreasing dose of ≤ 10 mg daily prednisone (or equivalent)
OR
 - iii) Patients with additional leptomeningeal metastases are eligible if they are treated and neurologically returned to baseline (except for residual signs or symptoms related to the CNS treatment) for at least 2 weeks prior to enrollment and have a life expectancy of at least 3 months. In addition, subjects must be either off corticosteroids or on a stable or decreasing dose of ≤ 10 mg daily prednisone (or equivalent)
- g) Patients must have evaluable disease by CT or MRI per RECIST 1.1 criteria (radiographic tumor assessment performed within 6 weeks of first dose of study drug) or clinically apparent disease that the investigator can follow for response.

Key exclusion criteria:

- h) Subjects with untreated, symptomatic CNS metastases are excluded.

Study Drug: includes both Investigational [Medicinal] Products (IP/IMP) and Non-investigational [Medicinal] Products (Non-IP/Non-IMP) as listed:

Study Drug for CA209172		
Medication	Potency	IP/Non-IP
Nivolumab Injection BMS-936558-01a	10 mg/mL; 100 mg/Vial; 10 or 5 vials per carton Open-label	IP

Study Assessments: Only data for the procedures and assessments specified in this protocol should be submitted to BMS on a case report form. Additional procedures and assessments may be performed as part of standard of care; however, data for these assessments should remain in the patient’s medical record and should not be provided to BMS unless specifically requested.

The following assessments should be monitored starting on Cycle 1 Day 1 and will continue as per the schedule in the Time and Events Table at the specified frequency until discontinuation from study therapy:

- Adverse events continuously throughout the study
- Physical examination and physical measurements including weight and ECOG PS

- Complete blood count with differential, including white blood cells, lymphocyte count, absolute neutrophil count, hemoglobin, hematocrit, and platelet count. Results to be obtained prior to dosing on infusion days.
 - Serum chemistry tests (blood urea nitrogen or serum urea level, serum creatinine, sodium, calcium, phosphate, chloride, glucose, lipase, and lactate dehydrogenase). Results to be obtained prior to dosing on infusion days. Amylase should be performed in addition to lipase in cases where lipase results are not available prior to dosing.
 - Liver function tests including aspartate aminotransferase, alanine transaminase total bilirubin, alkaline phosphatase, and albumin. Results to be obtained prior to dosing on infusion days.
 - Thyroid function testing includes thyroid stimulating hormone (free T3 and free T4 if abnormal results for TSH)
- During the 100 days after the last dose of the study treatment, patients will have 2 additional follow up visits to assess safety.

Efficacy assessments include initial mandatory tumor assessments at Week 12 (\pm 5 days). Further tumor assessments should be completed as required by local standards of care or at the investigator's discretion and are recommended every 8 weeks.

Changes in tumor measurements and tumor responses to guide ongoing study treatment decisions should be assessed by the investigator using RECIST 1.1.

Per Amendment 08, the EQ-5D-3L and survival follow up will be collected for up to 2 years from the first dose of study therapy or until death, withdrawal of study consent, or lost-to-follow-up as indicated in the assessment table.

Statistical Considerations:

Sample Size: With an approximate 15% screening failure rate, a cohort of 735 screened PS1 patients is projected to a yield 640 treated patients. With $n = 640$ patients, about 3 will experience a rare adverse event with 0.5% true cumulative event rate with a rate estimated within 95% confidence interval (CI) (0.2%-1.1%). Approximately 2 patients with events and a 95% CI of (0%-1.1%) for assumed true event rate of 0.3% are projected.

Endpoints: The primary endpoint is the incidence for high-grade (CTCAE v4.0 Grade 3 or higher), treatment-related, select adverse events.

The secondary endpoints include:

- Incidence of all high-grade (Grades 3 and higher), select adverse events
- Median time to onset and median time to resolution (Grades 3-4) of select adverse events
- OS
- Investigator-assessed ORR

[REDACTED]

[REDACTED]

[REDACTED]

[REDACTED]

[REDACTED]

Analyses: The evidence for the research hypothesis of this clinical trial that high-grade (CTCAE v4.0 Grade 3 or higher), treatment-related select adverse events occur with a low frequency in patients with advanced (unresectable or metastatic) melanoma will be presented in terms of the number, percentage of subjects, and 95% confidence interval for the percentage with these select adverse events during treatment and off-treatment overall and by cohort.

Adverse events from date of enrollment up to last contact with patients will be presented for the full study duration and separately for events that occur on- or post-treatment. In particular, safety data will be summarized and listed for all treated patients using the NCI CTCAE version 4.0. All on-study AEs, drug-related AEs, SAEs, and drug-related SAEs will be tabulated using worst grade per NCI CTCAE v4.0 criteria by system organ class and MedDRA preferred term. On-study laboratory parameters including hematology, chemistry, liver function, thyroid function, and renal function will be summarized using worst grade per NCI CTCAE v4.0 criteria.

Overall survival is defined as the time between the start of treatment and the date of death due to any cause. A subject who has not died will be censored at last known date alive.

OS will be summarized using Kaplan-Meier (KM) product-limit method and associated statistics. Median values of OS, if estimable, along with 2-sided 95% CI using the Brookmeyer and Crowley method will be calculated. Overall survival rates at selected time points, including survival rates at Years 1 and 2, together with their 95% CIs will also be estimated using KM estimates on the OS curves. Associated 2-sided 95% CIs will be calculated using the Greenwood formula. OS summary statistics by cohorts and subgroups will also be reported. OS will be further presented by initial investigator-assessed objective response under treatment with an anti-CTLA-4 monoclonal antibody.

ORR is defined as the number and percentage of patients with a best overall response (BOR) of confirmed CR or PR. ORR as assessed by the investigator will be reported.

TABLE OF CONTENTS

TITLE PAGE	1
DOCUMENT HISTORY	3
SYNOPSIS.....	5
TABLE OF CONTENTS.....	10
1 INTRODUCTION AND STUDY RATIONALE	13
1.1 Study Rationale.....	15
1.1.1 Rationale for Schedule and Nivolumab Dose.....	16
1.1.2 Rationale for Permitting Continued Treatment in Select Cases Despite Initial Progressive Disease.....	16
1.1.3 Rationales for Cohorts/Subgroups and Extension of Target Population	16
1.1.4 Rationale for Quality of Life Evaluation	18
1.2 Research Hypothesis.....	18
1.3 Objectives(s).....	18
1.3.1 Primary Objectives	18
1.3.2 Secondary Objectives.....	18
[REDACTED].....	[REDACTED]
1.4 Product Development Background.....	19
1.4.1 Clinical Activity of Nivolumab.....	19
1.4.1.1 Clinical Activity in Sequential Administration of Nivolumab After Ipilimumab (CA209-004).....	20
1.4.2 Adverse Effects with Nivolumab Therapy.....	21
1.4.3 Safety Aspects in Sequential Administration of Nivolumab After Ipilimumab (CA209-004):.....	24
1.5 Overall Risk/Benefit Assessment	25
2 ETHICAL CONSIDERATIONS.....	25
2.1 Good Clinical Practice	25
2.2 Institutional Review Board/Independent Ethics Committee.....	26
2.3 Informed Consent.....	26
3 INVESTIGATIONAL PLAN.....	27
3.1 Study Design and Duration.....	27
3.2 Post Study Access to Therapy.....	29
3.3 Study Population.....	30
3.3.1 Inclusion Criteria.....	30
3.3.2 Exclusion Criteria.....	34
3.3.3 Women of Childbearing Potential	[REDACTED]
[REDACTED].....	[REDACTED]

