8 STATISTICAL CONSIDERATIONS

The study will include patients with histologically confirmed stage III (unresectable) or stage IV melanoma and progression after prior treatment containing an anti-CTLA-4 monoclonal antibody treated with nivolumab (BMS-936558) at a dose of 3 mg/kg every 2 weeks. Patients will be treated with 3 mg/kg of nivolumab IV every 2 weeks for a maximum of 24 months.

Based on the Performance Status of the patients, there are 2 pre-defined cohorts: Cohort 1, enrolling patients with progression after prior treatment containing an anti-CTLA-4 monoclonal antibody and Performance Status 0-1 (n is at least 640, 85% of the minimum of the 735 screened) and Cohort 2, enrolling patients with progression after prior treatment containing an anti-CTLA-4 monoclonal antibody and Performance Status 2 (n is at the most 160, 85% of the maximum of the 185 screened; a minimum of 50 patients will be enrolled).

A patient who meets the screening criteria will be treated for a maximum of 24 months with safety follow-up at 30 [± 7] and 70-84 [± 7] days from first follow-up visit post-treatment. With an expected screening failure rate of 15%, a maximum total of about 800 patients (640 PS1 and 160 PS2) will be treated.

The number and percentage of patients with high-grade, treatment-related, select adverse events and their characteristics will be reported overall and by subgroups and during and off-treatment. Overall survival is defined as the time between the start of treatment and the date of death due to any cause. A patient who has not died will be censored at last known date alive. OS will be followed up while patients are on the study drug and every 3 months via in-person visits or phone contact after patients discontinue study drug.

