8.1 Sample Size Determination

Currently, there is only little reliable data describing the percentage of patients with melanoma progressing after prior therapy containing treatment with an anti-CTLA-4 monoclonal antibody, presenting with Performance Status 2, and eligible for nivolumab treatment. It is estimated that a minimum of 20% of the potential study population will initially present with PS2. Given that 20% of the 920 patients screened is 185 patients, it is expected that the full complement of 160 patients will be enrolled into the PS2 cohorts and treated.

With an approximate 15% screening failure rate, a cohort of 735 enrolled PS1 patients is projected to a yield 640 treated patients. With $n = 640$ patients, about 3 will experience a rare adverse event with 0.5% true cumulative event rate with a rate estimated within 95% confidence interval (CI) (0.1%-1.4%). Approximately 2 patients with events and a 95% CI of (0%-1.1%) for assumed true event rate of 0.3% are projected.

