8.4.2 Safety Analyses

8.4.2.1 Primary Analyses

The evidence for the research hypothesis of this clinical trial that high-grade (CTCAE v4.0 Grade 3 or higher), treatment-related select adverse events occur with a low frequency in patients with advanced (unresectable or metastatic) melanoma will be presented in terms of the number, percentage of patients, and 95% confidence intervals for the percentage with these select adverse events during and off-treatment overall and by cohort.

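### The synopsis gives a 95% CI of 0.2%–1.1% for a 0.5% event rate at n=640; Protocol 8.1 and SAP 5 give 0.1%–1.4% for the same inputs, and only the latter can be reproduced.

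*Protocol*

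**What the plan says.** The sample-size paragraph appears three times: in the protocol synopsis, in Protocol 8.1 and in SAP 5. All three use the same inputs. The synopsis reads: "With $n = 640$ patients, about 3 will experience a rare adverse event with 0.5% true cumulative event rate".

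The stated precision then differs:

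- Synopsis: "with a rate estimated within 95% confidence interval (CI) (0.2%-1.1" percent.
- Protocol 8.1: "with a rate estimated within 95% confidence interval (CI) (0.1%-1.4" percent. SAP 5 gives this same pair.

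All three places add the same companion figure, which the synopsis words as: "Approximately 2 patients with events and a 95% CI of (0%-1.1%) for assumed true event rate of 0.3% are projected".

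For the primary analysis, Protocol 8.4.2.1 plans counts, percentages and "95% confidence intervals for the percentage with these select adverse events during and off-treatment overall and by cohort". It includes no hypothesis test.

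**The concern.** One set of inputs and one confidence level cannot yield two different intervals by one method. Both versions are current text, and neither comes from an amendment log.

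The synopsis also looks wrong on its own terms. It prints an upper limit of 1.1% for a 0.5% rate and again 1.1% for a 0.3% rate, both at n=640. More expected events at the same n should push the upper limit up.

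In an estimation trial, the expected width of the interval is the statistical argument for the sample size. A reader who sees only the synopsis would believe that 640 patients bound a rare toxicity more tightly than they do.

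**Working it through.** **Inputs.** n = 640, true rate 0.5%, about 3 events, 95% confidence (synopsis, Protocol 8.1 and SAP 5). Expected events: 640 × 0.005 = 3.2. Companion case: rate 0.3%, about 2 events; 640 × 0.003 = 1.92.

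**Method.** The documents do not name a CI method for adverse-event percentages. SAP 7.5.1 names Clopper-Pearson, but only for response. Its limits for x events in n are:

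- lower = Beta quantile at 0.025 with parameters (x, n − x + 1)
- upper = Beta quantile at 0.975 with parameters (x + 1, n − x)

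**Step 1: reproduce Protocol 8.1 and SAP 5.**

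| Events / n | Clopper-Pearson 95% | Rounds to |
|---|---|---|
| 3 / 640 | 0.097%–1.364% | 0.1%–1.4% |
| 3.2 / 640 | 0.111%–1.410% | 0.1%–1.4% |
| 2 / 640 | 0.038%–1.124% | 0%–1.1% |
| 1.92 / 640 | 0.034%–1.104% | 0%–1.1% |

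One method explains both intervals in Protocol 8.1 and SAP 5, and the companion interval in the synopsis.

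**Step 2: try to reproduce the synopsis pair at n = 640, 95%.**

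| Method | 3 / 640 |
|---|---|
| Wilson | 0.160%–1.369% |
| Jeffreys | 0.132%–1.246% |
| Agresti-Coull | 0.092%–1.437% |
| Mid-P | 0.119%–1.270% |
| Logit | 0.151%–1.443% |
| Exact Poisson | 0.097%–1.370% |
| Wald | −0.060% to 0.998% |

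None rounds to 0.2%–1.1%. With 3.2 events the result is the same: Wilson 0.176%–1.415%, Jeffreys 0.147%–1.293%, Agresti-Coull 0.109%–1.481%, Wald −0.046% to 1.046%.

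**Step 3: try other sample sizes.** The planned treated total of 800 does not explain the pair: 4/800 (0.5%) gives 0.136%–1.275%. With Clopper-Pearson at a 0.5% rate, 0.2%–1.1% first appears at n of about 1,010 to 1,030. Some methods reach it at n = 920, the number screened (Wilson for 4/920: 0.169%–1.113%), or at 90% confidence (Jeffreys for 3/640: 0.170%–1.095%). Each of these contradicts a stated input.

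**Step 4: size of the discrepancy.**

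- Width: synopsis 1.1 − 0.2 = 0.9 points; exact 1.364 − 0.097 = 1.267 points. Ratio 0.9/1.267 = 0.71, so about 29% too narrow. Allowing for rounding of the printed limits, the width is 0.8 to 1.0, giving ratios of 0.63 to 0.79, or 21% to 37% too narrow.
- Confidence implied by the synopsis limits for 3 observed events: P(X ≥ 3 | 0.2%) = 0.138 and P(X ≤ 3 | 1.1%) = 0.079, so 1 − 0.138 − 0.079 = 0.783. The rounding range is 0.687 (limits 0.25%/1.05%) to 0.863 (limits 0.15%/1.15%). The same reading of 0.1%–1.4% gives 1 − 0.0272 − 0.0212 = 0.952.
- Upper limit in patients: 640 × 1.1% = 7.0; 640 × 1.4% = 9.0.

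**The case against.** The strongest objection is about weight. Protocol 8.1 and SAP 5 already carry the reproducible interval, and no threshold or decision rule uses the synopsis figure. The 0.5% rate illustrates a single rare event, not the pooled primary incidence, and the primary interval will come from observed data, so it cannot inherit the error. All of this stands, and it limits the consequence to a misstatement of precision.

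Second, the 29% depends on Clopper-Pearson, which is not named for adverse events. That also stands. Against other intervals for 3/640 the shortfall is about 19% (Jeffreys, 0.9/1.114), 22% (mid-P, 0.9/1.151), 26% (Wilson, 0.9/1.209) or 33% (Agresti-Coull, 0.9/1.345). The direction is the same each time. The 78% figure is likewise a tail-area reading for one observed count, not a general coverage probability.

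Third, the synopsis pair might be meant as a range of observed rates under a true rate of 0.5%: 1/640 to 7/640 is 0.16% to 1.09%, which prints as 0.2%–1.1%. This does not rescue it. The probability of 1 to 7 events is 0.9834 − 0.0404 = 0.943, short of 95%. The equal-tailed 95% range starts at 0 events. The companion 0%–1.1% fits a confidence interval for 2/640. The conflict with Protocol 8.1 and SAP 5 would also remain.

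**Conclusion.** The synopsis interval is wrong as written. For identical inputs it conflicts with Protocol 8.1 and SAP 5, and only 0.1%–1.4% can be reproduced. The synopsis overstates precision: measured against the exact interval it is about 29% too narrow, with an upper limit of 1.1% where 1.4% is correct.

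The conclusion that 0.2%–1.1% is not a 95% interval at n = 640 holds for every method tried. Only the size of the shortfall depends on taking Clopper-Pearson as the reference. How the synopsis figure arose is not documented. The practical effect is confined to what a reader of the synopsis is told about precision.

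**What to change.** In the synopsis, replace 0.2%–1.1% with 0.1%–1.4%, and leave 0%–1.1% for the 0.3% rate unchanged. It would help to name the CI method at the same time, for example exact Clopper-Pearson, which reproduces both intervals.

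The cost is one number pair in the synopsis. Enrolment, endpoints, analyses and the SAP interval do not change. The precision stated in the synopsis becomes less favourable. The correction goes through the usual revision route in Protocol 9.1.1.

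A separate, optional wording point in Protocol 8 does not affect this finding. Cohort 1 is described as "n is at least 640, 85% of the minimum of the 735 screened", but 0.85 × 735 = 624.75 and 0.85 × 185 = 157.25, whereas 640/735 = 87.1% and 160/185 = 86.5%. The simplest correction is to the percentage, since 640 stands in all three sample-size paragraphs. The same section treats 640 as a minimum and then counts it within "a maximum total of about 800 patients (640 PS1 and 160 PS2) will be treated"; these two uses should be reconciled.
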